## Sample size and statistical analyses

Assuming that staging intermediate and high risk PCa with  $^{18}\text{F}$ -PSMA PET/CT leads to upstaging in 20%, 398 patients, i.e. 199 patients in each arm, will be necessary to estimate the proportion of upstaged patients with  $^{18}\text{F}$ -PSMA PET/CT with sufficient precision as the expected length of the Wilson-score 95% CI for this proportion will be 11% (simulation study with N=2000 trials). These numbers are sufficient to indicate that the proportion of upstaged patients with  $^{18}\text{F}$ -PSMA PET/CT is statistically significantly larger than 12.9%

under above assumptions (power: 80%; two-sided testing; Type I error: 5%). A total of 448 patients (224 in each arm) are sufficient to indicate a statistically significant difference in progression free survival with assumed hazard rates of 0.35 and 0.5 for 18F-PSMA PET/CT and conventional staging respectively, implying a hazard ratio of 0.7. Estimates are based on a study duration of 4 years, consisting of 3 years accrual time and minimum follow-up period of 1 year before the first data collection, and a loss-to-follow-up of 10% (two-sample comparison of survivor functions; Exponential test; Type I error: 5%). Therefore, **448 patients (224 in each arm)** will be included in the study. For sample size calculation for the accuracy analyses planned in Group B only, we assumed a prevalence of metastases of 30%, sensitivity and specificity of 0.38 and 0.91 for conventional imaging, and 0.85 and 0.98 for PSMA-PET/CT. Then, a sample size of **128 patients** is sufficient to indicate a superior sensitivity for PSMA-PET/CT and a non-inferior specificity for PSMA-PET/CT, with a non-inferiority margin of 0.052, at a significance level of 5% (two-sided) with a power of 80%. We expect 224 patients from OUH, 80 patients from Hospital of Little Belt, 72 patients from Hospital of South West Jutland and 72 patients from Hospital Sønderjylland. Patients from Hospital Sønderjylland will have their scans performed in either Hospital of Little Belt or OUH Odense.

Primary analyses will be done as indicated in the sample size rationale above. Cox proportional hazard regressions will be adjusted for available demographic and clinical baseline variables, and graphical displays will comprise Kaplan-Meier plots including risk tables (i.e. patients at risk in each group).

Descriptive statistics will be done according to data type (mean±SD or median (range) for symmetrically and unsymmetrically distributed continuous variables, respectively, as judged visually with histograms including approximating Normal curves; frequencies and percentages for categorical variables). Exploratory, bivariate testing will be done with unpaired t-tests or, alternatively, Wilcoxon's rank sum test on continuous and Chi-squared test, alternatively, Fisher's exact test for categorical variables. Level of significance will be 5%. All analyses will be done with STATA/IC 15 (StataCorp, College Station, Texas 77845 USA). If exceptions for this statistical plan is needed, it will be reported when published.

Missing data will be reported in the publications. Illegitimate data will be excluded. Reason for un-used data will be reported.

The primary analysis of QoL and morbidity will be based on the changes in the FACT-P questionnaire at the timepoints: inclusion and 12 months. An 8-point decline in the global FACT-P score will be considered clinically relevant. The secondary analyses include the group difference in a repeated measurement analysis, making use of data collected at the several time points of FACT-P. Secondary analyses will likewise be conducted using the EQ-5D-5 and EPIC-26. The time from baseline to decline of 8 points in global FACT-P score will be visualized by Kaplan-Meier plots and explored with a two-sided log-rank test. The level of significance will be 5%. All analyses will be done with STATA/IC 15 (StataCorp, College Station, Texas 77845 USA).

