Biopsy of suspected metastatic lesions in N- and M-positive patients (suspicion of metastases) as well as lymph node specimen in N- and M-negative patients will be intended as reference standard in both groups as well as a nadir unmeasurably low post-surgery prostate specific antigen blood sample to indicate no residual disease where applicable. Reference standard in the accuracy analysis of F-PSMA PET/mpMRI with regard to T- staging is histopathology on surgical specimen. As the risk of distant metastases increases with increasing PSA-levels, analyses will be performed on both population level as a whole as well as in two PSA-strata with cut-off being PSA=100 ng/ml.

Treatment and subsequent follow-up will be planned on the basis of the results of the scans and according to current guidelines (1, 5).

Follow-up data will be collected from patient journals by the researcher/principal investigator or a delegate, and will consist of clinical information, examination reports, blood test results, information about treatments and pathology reports, all performed in a clinical setup as determined by the clinician. No extra visits, scans or blood test are required except for questionnaires. The patients will be asked to fill in questionnaires (EQ-5D-5L, FACT-P and EPIC 26) concerning quality of life during at baseline and 3, 6, 12, 24, 60, 120 og 236 months after recruitment. The questionnaires will be delivered to the patients e-boks from REDCap automatically at the specific time points. All collected information will be used in this project for analysis of treatment decision, relapse detection, overall survival and quality of life in the two patient groups.

Primary endpoints (Group A vs. B)

1. Treatment strategies and progression-free survival
2. Quality of life measures

Secondary endpoints

1. Overall survival (Group A vs. B)
2.  $^{18}\text{F}$ -PSMA-PET/MR for evaluation of extension of tumor in the prostate gland and surrounding structures compared to histopathology on surgical specimen.
3. Accuracy of  $^{18}\text{F}$ -PSMA-PET/CT compared to NaF-PET/CT for evaluation of bone metastases

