Four publications are planned, cf. section "Planned publications" below. Studies 1 and 4 will address the presumed patient benefit from staging with  $^{18}\text{F}$ -PSMA PET/CT in a randomized design, and outcome measures will consequently be impact on stage migration, treatment decision, progression free survival, and time to relapse in group A vs. group B. As studies 2 and 3 are comparative studies, outcome measures in this setting will be accuracy measures regarding N- and M-staging in study 2, and T- and R-staging as well as change in treatment intend in study 3.

Beyond the scope of this PhD-project we plan a follow-up time period of up to 20 years for analysis of disease free period, overall survival and quality of life.

Admittance to documents and data including patients journals are given to the relevant GCP-units and the Danish Medicines Agency for monitoring, audition and inspection of the project.

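### The test of upstaging against a fixed 12.9% does not require upstaging to be confirmed, so it cannot separate better staging from more false-positive readings

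*Combined protocol and SAP*

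**What the plan says.** In *Sample size and statistical analyses*, the plan assumes that PSMA PET/CT "leads to upstaging in 20%, 398 patients, i.e. 199 patients in each arm". It justifies that number first by precision: "the expected length of the Wilson-score 95% CI for this proportion will be 11"%. It then adds a one-sample test: "These numbers are sufficient to indicate that the proportion of upstaged patients with" PSMA PET/CT "is statistically significantly larger than 12.9"%, "under above assumptions (power: 80%; two-sided testing; Type I error: 5"%). The same section later states: "Primary analyses will be done as indicated in the sample size rationale above". The final size is 224 per arm, set by progression-free survival.

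In *Research plan*, studies 1 and 4 address presumed patient benefit, and their "outcome measures will consequently be impact on stage migration, treatment decision, progression free survival, and time to relapse in group A vs. group B". The same section intends a reference standard in both groups: "Biopsy of suspected metastatic lesions in N- and M-positive patients (suspicion of metastases) as well as lymph node specimen in N- and M-negative patients", plus post-surgery PSA where applicable. That standard is not tied to upstaging.

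The plan does not define upstaging, name the stage it is measured from, give the origin of 12.9%, or say whether an upstaged case must be confirmed. The list of primary and secondary endpoints does not name upstaging.

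**The concern.** As described, the test needs only a count of upstaged men in one arm. If unconfirmed readings are counted, a false-positive lesion contributes as much as a real metastasis, and less specific reading makes the 12.9% mark easier to pass. Replacing the fixed benchmark with group A does not cure this by itself, because a comparison of unverified upstaging also rewards false positives.

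What is at stake is the conclusion of study 1, on stage migration and treatment strategy. It could report a favourable result for a scan that finds no more disease. In the other direction, if PSMA PET/CT performs as assumed, false positives in group A would hide part of a real gain.

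**Working it through.** **Inputs from the sample size section.** Upstaging 20%, benchmark 12.9%, n = 199 (final 224 per arm), two-sided 5%. Prevalence of metastases 30%; sensitivity/specificity 0.38/0.91 for conventional imaging and 0.85/0.98 for PSMA PET/CT. The plan sets these last figures for the 128-patient Group B accuracy analysis; they are borrowed here.

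**The plan's own figures.** Normal approximation: power = Φ[(0.20 − 0.129 − 1.96·√(0.129·0.871/199)) / √(0.20·0.80/199)] = Φ[(0.071 − 0.0466)/0.0284] = 80.6%, against 80% stated. The expected Wilson interval length at 20% is 11.03%, against 11% stated. Both reproduce. As rejection rules:

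- Wilson lower limit above 12.9%: at least 35/199 or 39/224. Power at 20% is 82.6% and 85.4%.
- Exact binomial: at least 36/199 or 40/224. Power at 20% is 77.5% and 81.1%.

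**A scan with only conventional accuracy (0.38/0.91).** Since upstaging is undefined, three definitions are tried.

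- (a) Every positive reading counts (pre-imaging stage assumed N0 M0): 0.30·0.38 + 0.70·0.09 = 0.114 + 0.063 = 17.7%.
- (b) PSMA-positive and conventional-negative in the same men, readings conditionally independent: 0.30·0.62·0.38 + 0.70·0.91·0.09 = 12.8%.
- (c) Confirmed true positives only: 0.30·0.38 = 11.4%.

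| Definition | Upstaged | Pass, n = 199 (exact / normal / Wilson) | Pass, n = 224 |
|---|---|---|---|
| (a) | 17.7% | 47% / 52% / 55% | 50% / 56% / 57% |
| (b) | 12.8% | 2.0% / 2.2% / 3.2% | 1.8% / 2.2% / 2.8% |
| (c) | 11.4% | 0.4% / 0.3% / 0.6% | 0.3% / 0.3% / 0.5% |

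Under (a), the 6.3 points of false positives carry the scan past 12.9%. The result depends on prevalence: by the Wilson rule it is 16% at prevalence 20%, 33–35% at 25% and 74–77% at 35%. Under (b), positive correlation between readings lowers the pass rate further (correlation 0.25: 9.6% upstaged, pass below 0.1%). Under (c), the planned PSMA accuracy gives 0.30·0.85 = 25.5% and passes more than 99% of the time.

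**Lower specificity, sensitivity unchanged at 0.38.**

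- (a), specificity 0.88: 0.114 + 0.70·0.12 = 19.8%; Wilson pass 81% (n = 199) and 84% (n = 224). At 0.85: 94% and 96%.
- (b), specificity 0.80: 0.30·0.62·0.38 + 0.70·0.91·0.20 = 19.8%; Wilson pass 81% and 84%.

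These are close to the 83–85% the same rule gives at the planned 20%.

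**Group A vs. group B** (two-proportion z-test, 224 per arm, two-sided 5%, definition (a) unless confirmed).

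- Sensitivity 0.38, specificity 0.80 in B: 17.7% vs 0.114 + 0.70·0.20 = 25.4%; significant 51% of the time with no extra disease found.
- Planned accuracies, upstaging as read: 17.7% vs 0.255 + 0.014 = 26.9%; power 65%.
- Planned accuracies, confirmed: 11.4% vs 25.5%; power 97%. If both arms verify 80% of true positives, 92%; if 60%, 82%.

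**The case against.** - **Scan readings only.** A reader might infer that the plan counts upstaging from readings alone. The documents do not say so. They are silent, and they intend a reference standard in both groups. The supportable statement is that confirmation is not required.
- **A 55% pass rate on the plan's own inputs.** This is also tempting and not supported. It needs definition (a), which the plan never states, and figures set for another analysis. Definition (a) does not fit the plan's 20% either: planned PSMA accuracy would give 26.9%. Definition (b) gives 0.30·0.62·0.85 + 0.70·0.91·0.02 = 17.1% with independent readings (14.1–20.0% depending on correlation), which is nearer, and there an equally accurate scan rarely passes. Definition (a) stays plausible because only a subgroup of group B has the blinded NaF-PET, so a same-man comparison is not assured.
- **Role of the test.** Upstaging is not a listed endpoint, precision comes first in the justification, and no success criterion is named. This stands in part: the test enters the primary analyses only through the cross-reference to the sample size rationale.
- **The accuracy analysis.** The 128-patient analysis seeks superior sensitivity and non-inferior specificity (margin 0.052). In a simulation with independent readings, McNemar's test for sensitivity and a Wald limit for specificity, a 0.38/0.91 scan meets both about 0.7% of the time, and 0.2% or less at specificity 0.88 or lower. That analysis would expose such a scan, but it belongs to study 2 and does not change what study 1 may report.
- **Confirmed-only upstaging.** Treatment follows the scan results, so stage as read is a legitimate measure of clinical impact. Unequal biopsy rates can also distort confirmed counts. Under the planned accuracies, verifying 80% in A and 60% in B (9.1% vs 15.3%) cuts power to about 52%. With equal sensitivity of 0.38, verifying 50% in A and 90% in B (5.7% vs 10.3%) gives a false gain 43% of the time. These rates are illustrative; the documents give none. This objection stands and shapes the fix.

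**Conclusion.** The point holds in a limited form. A one-arm test of upstaging against an unsourced 12.9%, with no requirement for confirmation, cannot distinguish more accurate staging from more false-positive readings. How easily a scan with conventional accuracy would pass depends on a definition the plan does not give: about 47–57% if all positives count, 2–3% for discordant independent readings, and under 1% if only confirmed cases count. The direction does not depend on the choice between the two unverified definitions: less specific reading raises the pass rate in both, to 81–84% in the cases shown. All these sizes rest on the borrowed Group B inputs, and those under (b) also on conditional independence. It should be corrected before analysis; it does not invalidate the trial, whose size is set by progression-free survival.

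**What to change.** In *Sample size and statistical analyses* and in the description of study 1:

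1. Do not use an unverified proportion above 12.9% as a success criterion. Keep the one-arm proportion and its Wilson interval as a precision statement.
2. Analyse stage migration as group A vs. group B, as *Research plan* describes, with upstaging measured from the same pre-imaging clinical stage in both arms.
3. Report upstaging by arm split into confirmed, refuted and unverified against the intended reference standard, with the verification rate per arm.
4. Present confirmed upstaging beside upstaging as read, with best-case and worst-case handling of unverified lesions. Base any claim of more accurate staging on the confirmed results.
5. Do not make confirmed-only upstaging the sole outcome.

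The cost is protocol and SAP wording and slightly more analysis, using reference-standard data already intended. Verification will not be complete, so confirmed proportions will be lower than those as read and sensitive to unequal biopsy rates between arms.

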## Research plan

The study is planned in a prospective randomized controlled design as illustrated in appendix 1 and 2 and will be carried out in close collaboration with the Department of Urology. The patients will be included and randomized as a part of one of the initial doctors appointments in a consultation room, and they will be encouraged to bring a relative to this consultation. Patients are identified when they have an appointment at Department of Urology, and the researchers will be given information from the clinicians, which means that they will not access the patient journals before enrolling. The patients will be informed about the project from the PhD-student, a physician from the Nuclear Medicine Departments, an Urologist from the cooperating departments or a nurse involved in the project, all with expertise in prostate cancer. They will be offered time to consider enrolment in the trial. The patients will be offered further information and answering of upcoming questions over the telephone after the initial talk. At this time or one of the following days, when they have accepted to be enrolled in the project and signed the written consent, they will be randomized in REDCap, where the randomisation code is kept. The randomization will be stratified according to the patients clinical risk status and pathology of biopsies. The written consents will be collected at the Nuclear Medicine Department, when they meet for their scan and at the earliest the day after the information in Department of Urology. Our study population will comprise men with a newly diagnosed intermediate or high risk (including locally advanced) PCa (1) or with a clinical suspicion of metastases based on other findings. Included patients will be randomized into a control group (A) and an interventional group (B). Group A will be staged by conventional imaging, i.e. CE-CT for N-staging and NaF-PET for M-staging. Group B will be staged by F-PSMA PET/CT for both N- and M-staging. A subset of patients with risk of extracapsular extension considered for radical prostatectomy in group B will also have an F-PSMA-PET/mpMRI-scan for T-staging (evaluation of the tumor). This scan will be performed in continuation of the F-PSMA-PET/CT, i.e. on the same administered dose of F-PSMA. Furthermore, a subgroup of patients in group B will have a blinded NaF-PET-scan for the purpose of performing comparative accuracy analyses.

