## Planned publications

1. Clinical impact on stage migration and treatment strategy when using 18F-PSMA PET/CT compared to conventional imaging in primary staging of PCa (Group A vs B).

2. A prospective comparative accuracy study of 18F-PSMA PET/CT for N- and M-staging compared to conventional imaging in primary PCa (Group B).
3. The added value of PSMA-PET/mpMRI compared to PSMA-PET/CT on T, N, and R-staging (R = resection level) (Subgroup of B).
4. The impact on progression free survival and biochemical relapse when using 18F-PSMA PET/CT compared to conventional imaging in primary staging of PCa (Group A vs. B - planned as a joint publication with PhD student from the Department of Urology).

It is the intention to publish the results no matter if they are positive, negative or inconclusive. The results will be published in [www.clinicaltrialsregister.eu](http://www.clinicaltrialsregister.eu).

Authorship order will be depending on work effort and involvement according to the Vancouver Declaration (IMJCE). No clauses agreed.

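### Is the accuracy sample size of 128 patients at 80% power inconsistent with its own inputs, or aimed at the wrong endpoint?

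*Combined protocol and SAP*

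**What the plan says.** The accuracy calculation is in the section Sample size and statistical analyses. The assumptions are "we assumed a prevalence of metastases of 30%, sensitivity and specificity of 0.38 and 0.91 for conventional imaging", with 0.85 and 0.98 for PSMA-PET/CT. From these the section states that 128 patients suffice for two aims together, higher sensitivity and non-inferior specificity, "with a non-inferiority margin of 0.052" and "at a significance level of 5% (two-sided) with a power of 80"%. The paired test, the dependence between the errors of the two scans, and the division of the 5% and the 80% between the aims are not given.

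The Research plan defines conventional imaging as "CE-CT for N-staging and NaF-PET for M-staging". It adds that "a subgroup of patients in group B will have a blinded NaF-PET-scan for the purpose of performing comparative accuracy analyses". The outcomes listed there include "accuracy measures regarding N- and M-staging in study 2", and Planned publications describes that study as a "comparative accuracy study of 18F-PSMA PET/CT for N- and M-staging compared to conventional imaging". Secondary endpoint 3 is narrower: accuracy of PSMA-PET/CT "compared to NaF-PET/CT for evaluation of bone metastases".

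**The concern.** There are two reasons to stop at this paragraph.

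- **The figures.** Take two-sided 5% for each aim and put the stated values through standard paired formulas. The power at 128 for both aims together is then well above 80% whatever the dependence between the scans, and 80% is reached with fewer patients. An N and a power that do not belong together suggest that some other input was used, and would leave the 0.052 margin without a visible basis.
- **The endpoint.** This is the only accuracy sample size in the plan, and endpoint 3 is the only listed endpoint on the accuracy of PSMA-PET/CT. A reader might join the two. The assumed 0.38 cannot describe NaF-PET in bone: the Background section gives bone scintigraphy 80% sensitivity and rates NaF-PET above it. If 128 were taken as the size for endpoint 3, the bone comparison would look far better powered than it is, and a non-significant difference might be taken as equivalence.

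**Working it through.** **Inputs**, all from Sample size and statistical analyses: prevalence 0.30; sensitivity 0.85 v 0.38; specificity 0.98 v 0.91; margin 0.052; 5% two-sided; N = 128. Expected numbers are 128 × 0.30 = 38.4 with metastases and 128 × 0.70 = 89.6 without.

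**Dependence.** Let b be the probability that PSMA-PET/CT is right and the comparator wrong, and c the reverse; d = b − c and ψ = b + c. The plan gives no discordance, so the feasible range is used.

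| Dependence | Sensitivity b, c | Specificity b, c |
|---|---|---|
| Nested (minimum discordance) | 0.47, 0 | 0.07, 0 |
| Independent | 0.527, 0.057 | 0.0882, 0.0182 |
| Maximum discordance | 0.62, 0.15 | 0.09, 0.02 |

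**Formulas.**

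- Sensitivity (McNemar): diseased n = (z_α√ψ + z_β√(ψ − d²))² / d², then divide by 0.30.
- Specificity (paired non-inferiority): non-diseased n = (z_α + z_β)²(ψ − d²) / (d + 0.052)², then divide by 0.70.

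**Reading 1: full two-sided 5% for each aim.** The last column uses an exact McNemar test, a random number of diseased patients and the normal formula for specificity.

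| Dependence | Sensitivity power at 128 | Specificity power at 128 | Joint (product) | Joint (exact McNemar) |
|---|---|---|---|---|
| Nested | 99.9% | 99.5% | 99.4% | 99.4% |
| Independent | 99.1% | 95.2% | 94.3% | 93.5% |
| Maximum | 94.6% | 94.5% | 89.5% | 85.9% |

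On this reading joint power is 86 to 99%. Joint 80% needs 64, 94 or 115 patients by the exact method (62, 89 or 105 by formula). The stated pair is not reproduced.

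**Reading 2: the single 5% shared over the two aims (2.5% two-sided each), 90% power per aim so that joint power is at least 80%, maximum discordance.** Here z_α = 2.2414 and z_β = 1.2816.

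- Sensitivity: d = 0.47, ψ = 0.77, ψ − d² = 0.5491. n = (2.2414 × 0.8775 + 1.2816 × 0.7410)² / 0.2209 = 38.5, so N = 38.5 / 0.30 = 128.4.
- Specificity: d = 0.07, ψ = 0.11, ψ − d² = 0.1051. n = (3.5230)² × 0.1051 / (0.122)² = 87.6, so N = 87.6 / 0.70 = 125.2.
- At 128 the powers are 89.9% and 90.7%; jointly 0.899 × 0.907 = 81.5%. With exact McNemar and a random number diseased, joint power is 77.9%. Joint 80% by formula is reached at 125.

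Every printed input is kept, and the stated pair is reproduced to within 3% on N and about 2 points on power.

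**Which endpoint.** The sample-size text speaks of metastases in general and of conventional imaging, which the Research plan defines as CE-CT plus NaF-PET. Study 2 compares PSMA-PET/CT with conventional imaging for nodal and metastatic staging. The Background section reports about 40% sensitivity for CE-CT or MR in nodes, which is close to 0.38. All of this points to study 2. No sentence links 128 to endpoint 3, and endpoint 3 states no superiority aim, margin or power.

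**What would follow for bone if the link were made.** The plan prints no NaF-PET sensitivity, no PSMA-PET/CT sensitivity in bone and no bone prevalence. Assume 0.80 v 0.85 and 38 bone-positive patients; 38 is an upper expectation, because 30% covers any metastasis. Exact McNemar power is 1 to 4% (7 to 28% by normal approximation), and the 95% CI half-width for the difference is 7 to 19 points. With 0.80 v 0.95 the exact power is 34 to 52%. These figures show only that 128 should not be carried over to endpoint 3, which the plan does not do.

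**The case for a change.** The strongest reply is that Reading 2 is supplied by the reader. The plan prints one 5% and one 80%. When both aims must succeed, no alpha split is needed. Maximum discordance is an extreme: no patient with metastases would be missed by both methods. With the same split, independent errors give 88 to 90% joint power and nested errors about 99%. A different route also lands on 128: it sets specificity at 0.98 for both methods and uses a one-sided 5% test, which ignores the stated 0.91 and the stated sidedness. The route actually used therefore cannot be established.

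The same section says that primary analyses follow the sample-size rationale, yet it names no accuracy test. The bivariate tests listed afterwards are all for unpaired data, while this comparison is paired. The size of the NaF-PET subgroup is not stated outright either.

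All of this stands as a remark on documentation. It does not show that 128 and 80% are incompatible, because one conservative choice that the text leaves open reproduces them. The unpaired tests are listed for exploratory work, and a statistician comparing two scans in the same men would use a paired method. The natural reading of the subgroup is about 128, since those scans are done for the analyses that this number sizes.

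**Conclusion.** The concern does not call for a change. The 86 to 99% joint power is correct if each aim takes the full two-sided 5%. If the 5% is shared, with 90% power per aim and maximum discordance, joint power at 128 is about 78 to 82%, in line with the stated 80%. The plan does not choose between these readings, so no error is demonstrated. On the first reading 128 is more than sufficient, and the total of 448 comes from the progression-free survival calculation, so nothing else depends on it.

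The endpoint worry needs a link that the plan does not make. The wording points to the study 2 staging comparison, and endpoint 3 is a secondary descriptive comparison with no power claim. The bone figures rest on assumed inputs and cannot count against the design.

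What is left is a gap that analysts fill sensibly: a paired analysis for study 2, and for endpoint 3 paired differences with 95% confidence intervals, without reading a non-significant result as equivalence. Following the plan as written gives no wrong result. This conclusion rests on normal-approximation and exact McNemar calculations over the feasible range of dependence, because the plan states neither the test nor the discordance.

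### The primary FACT-P comparison states no baseline adjustment or missing-data method and leaves the 3- and 6-month forms unused; a baseline-adjusted mixed model would be more precise and better protected

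*Combined protocol and SAP*

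**What the plan says.** Under Research plan, the second primary endpoint for Group A vs. B is "Quality of life measures". Questionnaires, FACT-P among them, are sent "at baseline and 3, 6, 12, 24, 60, 120 og 236 months after recruitment", so two forms fall between the two time points of the primary comparison.

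Under Sample size and statistical analyses:

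- On the primary comparison, the plan writes: "The primary analysis of QoL and morbidity will be based on the changes in the FACT-P questionnaire at the timepoints: inclusion and 12 months".
- As the threshold for an individual patient, it sets: "An 8-point decline in the global FACT-P score will be considered clinically relevant".
- For the use of the remaining forms, it plans: "The secondary analyses include the group difference in a repeated measurement analysis, making use of data collected at the several time points of FACT-P".
- On gaps in the data, it offers only this: "Missing data will be reported in the publications". For anything left out of an analysis, it adds: "Reason for un-used data will be reported".

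That section adjusts the Cox regressions for baseline variables but says nothing comparable for FACT-P. For the primary FACT-P comparison it names no test, model, population or imputation rule. For the secondary repeated-measures analysis it gives no model type, covariance structure, handling of baseline or target visit.

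**The concern.** A change score needs both values. With no method for filling a gap, a man who returned forms at inclusion, 3 and 6 months but not at 12 months would drop out of a primary-endpoint comparison. Two things are then at stake.

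**Precision.** A simple change score uses the baseline less efficiently than a model that adjusts for it. The trial was not sized on FACT-P, so there is no stated margin to give away.

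**Bias.** The trial expects the arms to differ in treatment strategy and progression (Problem, aim, and hypothesis). If the planning hazard rates of 0.35 and 0.5 are per year, 1 − exp(−0.35) = 30% and 1 − exp(−0.5) = 39% of men would have progressed by month 12, when the primary form is due. If worsening health or treatment burden affects response, the men left in the comparison may be selected differently in the two arms. The documents do not say that this will happen. They also give no means of dealing with it.

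**Working it through.** **1. The plan's own figure.** The documents give no FACT-P sample size, power, SD, correlation or non-response rate. The only figure is 448 (224 per arm), set by progression-free survival. It reproduces with hazards 0.35 and 0.5, 3 years' uniform accrual plus 1 year, two-sided 5%, and 80% power (assumed, since power is not restated there). The event probability per arm is 1 − [exp(−h) − exp(−4h)]/(3h), which gives 0.564 and 0.686, mean 0.625. The exponential test needs 402 men before loss, and 402/0.9 = 447. So 448 is sound for its purpose but says nothing about FACT-P.

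**2. Effect of baseline adjustment.** Let s be the SD of FACT-P at each visit and r the baseline-to-12-month correlation.

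- Change score: variance 2s²(1 − r).
- Baseline-adjusted 12-month score: variance s²(1 − r²).
- Ratio: (1 + r)/2.

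| Assumed r | Variance ratio | Equivalent increase in patients |
|---|---|---|
| 0.4 | 0.70 | 1/0.70 = 1.43, i.e. 43% |
| 0.5 | 0.75 | 1/0.75 = 1.33, i.e. 33% |
| 0.6 | 0.80 | 1/0.80 = 1.25, i.e. 25% |
| 0.7 | 0.85 | 1/0.85 = 1.18, i.e. 18% |

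An illustration, with all inputs assumed: s = 15, r = 0.6, true difference 4 points, 20% missing at 12 months (224 × 0.8 ≈ 179 per arm).

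- Change score: SE = 15 × √(0.8 × 2/179) = 1.42, power 81%, detectable difference at 80% power 3.97.
- Baseline-adjusted: SE = 15 × √(0.64 × 2/179) = 1.27, power 88%, detectable difference 3.55.

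With s = 20 the powers are 56% and 66%.

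**3. What months 3 and 6 add to precision.** A simulation used 224 per arm, visits at 0, 3, 6 and 12 months, equal correlation between visits, s = 15, a true difference of 4 points and dropout after month 3. A repeated-measures model without baseline adjustment had a variance ratio to the change score of 1.00 with complete data and about 0.92 to 1.00 with dropout. Once baseline was in the model, months 3 and 6 cut the variance by only about 0% to 8% more. Most of the precision gain therefore comes from the baseline term.

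**4. What they add against bias.** In the same simulation, dropout depended on the decline already recorded, but in the control arm only. Per-interval dropout was set at 5% or 11%. It was constant in the other arm, and in the control arm it rose with the recorded decline. The bias in the 12-month difference (true value 4) was:

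| Assumed r | Completer change score, 5% | Completer change score, 11% | Likelihood-based repeated measures |
|---|---|---|---|
| 0.4 | −2.14 | −3.38 | about 0 |
| 0.6 | −1.33 | −2.25 | about 0 |
| 0.7 | −0.93 | −1.68 | about 0 |

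Here "about 0" would be too strong a claim for real data; it means 0.02 points or less in these runs, against a simulation error of roughly 1.7/√3000 = 0.03. When the same dropout rule applied in both arms, the change-score bias was only about −0.1 to −0.3.

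**The case against.** A 12-month change is a legitimate primary target, and the plan already prespecifies repeated measures and time to an 8-point decline as supporting analyses. Reordering planned analyses can look like preference. That would be a fair reply if the primary method were specified, but it is not. The recommendation also keeps the 12-month target and changes only how it is estimated.

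Three stronger readings are tempting, and the documents do not support them.

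- **A reader might infer that the plan prescribes an unadjusted complete-case analysis.** It does not. It is silent on model and population, and a change analysis with baseline as a covariate would fit its wording. The unpaired t-test it names belongs to exploratory testing.
- **A reader might infer that the planned secondary analysis is already the more precise one.** Its model and baseline handling are not given. Without baseline adjustment and with complete data, its 12-month contrast equals the change score. It could also be an average over visits, or a classical analysis that deletes incomplete cases and so loses the protection against dropout.
- **A reader might put a number on the men lost.** No FACT-P non-response rate is given. The only loss figure, 10%, is for progression-free survival.

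The bias argument is conditional too. Questionnaires are sent electronically and do not depend on attending a visit, and dropout driven by decline in one arm only is an extreme case. This limits the likely size of the bias but does not remove the exposure.

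**Conclusion.** The point holds as a weakness in the analysis of a primary endpoint that should be corrected; it does not invalidate the trial. As written, the primary FACT-P comparison leaves the 3- and 6-month forms unused, states no baseline adjustment, and only reports missing data.

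The precision gain is a variance reduction of about 15% to 30% for an assumed r of 0.7 to 0.4, measured against a simple change score. If the sponsor already intends baseline as a covariate, that gain is already secured and only needs to be written down.

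The bias is about 0.1 to 0.3 points if dropout works alike in both arms. It is about 0.9 to 3.4 points in the one-arm scenario, against an assumed true difference of 4. These figures rest on assumed SD, correlations, difference and dropout. The plan's 8 points define a decline in one patient, not a difference between arms, so they are no direct yardstick for this bias. The protection from a mixed model holds only if data are missing at random.

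**What to change.** In Sample size and statistical analyses, define the primary FACT-P analysis as a likelihood-based mixed model with visit, arm-by-visit and randomisation-strata terms. Name the 12-month arm difference with its 95% CI as the target.

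State how baseline enters, by one of two routes:

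- Put baseline in the outcome vector with arm means constrained equal, so that every man with at least one FACT-P form is included.
- Use baseline as a covariate, and state who is then excluded: men with no baseline form or no later form. This version cannot include all randomised men.

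Keep the simple 12-month change as a sensitivity analysis. Add one missing-not-at-random analysis, for example one that lowers the assumed scores of non-responders by a range of amounts in each arm separately.

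The cost is a few lines of text and slightly more analysis work, with no new data or software. The drawback is reliance on missing at random, which the added sensitivity analysis probes. The change should be dated and made before FACT-P scores are examined by arm, so that the choice cannot appear driven by results.
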